### 2.2 Objectives

The primary aim of this trial is to evaluate the effectiveness of a culturally adapted intervention that combines in-person counseling with mobile health (mHealth) support to improve adherence to PrEP medication among GBMSM in Romania. This population faces

substantial barriers to HIV prevention, including stigma and limited access to PrEP. By hypothetically increasing adherence, the intervention tested in this study seeks to mitigate HIV transmission risks within this high-risk group, ultimately contributing to public health initiatives targeting HIV prevention.

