# 3. Study Methods

### 3.1 Trial Design

The Prepare Romania trial is a two-arm, parallel-group randomized controlled trial (RCT) with a 1:1 allocation ratio, designed to evaluate the effectiveness of a culturally adapted intervention to improve adherence to PrEP among GBMSM in Romania. Participants are randomized to either the intervention or control arm. The intervention arm includes a combination of counseling and a culturally tailored mobile health app that supports PrEP adherence. Participants in the control arm receive standard PrEP education only. Randomization is stratified by city (Bucharest and Cluj-Napoca), and the study is unmasked, with both participants and staff aware of group assignments. Primary and secondary outcomes will be collected at baseline, 3 months, and 6 months post-randomization.

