### 3.2 Randomization

Upon completing informed consent and screening, participants in the Prepare Romania trial are randomized to either the intervention arm (Prepare Romania) or the control arm (PrEP education-only). This randomization process is managed by the study coordinator using a computerized algorithm that ensures a 1:1 allocation ratio. The trial aims for 60 participants per city (Bucharest and Cluj-Napoca), but the randomization sequence accommodates up to 70 participants per city. This approach provides flexibility, allowing for up to 10 potential exclusions after the initial medical visit due to PrEP contraindications or personal choices to forgo PrEP initiation based on clinical assessments. The study's randomization plan does not involve additional stratification factors outside the city-level allocation.

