# 3.3 Sample Size

The Prepare Romania trial's sample size was chosen to provide preliminary data on the hypothesized intervention outcomes, PrEP adherence and persistence among GBMSM in Romania, as well as to inform the design of a future effectiveness trial. A formal power calculation was not conducted due to the exploratory nature of this pilot study. Instead, we followed guidance from Whitehead et al., which provides recommendations for sample sizes in pilot studies.

The sample size of 60 participants per arm (120 total) was selected based on conservative effect size estimates drawn from previous studies evaluating PrEP adherence interventions. In a comparable RCT testing the SPARK intervention, protective PrEP levels (defined as adherence of ≥4 doses per week) were observed in 94% of the intervention arm and 85% of the control arm at the 3-month follow-up, with corresponding rates of 92% and 86% at 6 months. This difference in adherence rates translates to an estimated effect size of 6%, with a pooled standard deviation of approximately 0.32, yielding a standardized effect size of 0.19. Whitehead et al. suggest a minimum sample size of 25 participants per condition for pilot trials when the effect size falls between 0.1 and 0.3. To ensure adequate power, the Prepare Romania trial conservatively enrolls 60 participants per arm, exceeding this minimum and allowing for a robust assessment of intervention impact.

Each site (Bucharest and Cluj-Napoca) is tasked with recruiting 60 participants. With this sample size, the study expects retention at 6 months to exceed 25 participants per arm, even accounting for potential attrition. This estimate is supported by high retention rates (approximately 89%) reported in prior SPARK trials.

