# **4.2** Analysis Populations

The primary analysis for the Prepare Romania trial will follow the intention-to-treat (ITT) principle.

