# **Primary Outcome**

The primary outcome, PrEP adherence obtained through DBS, is a binary variable and will be analyzed using a GLMM with a logit link function. The intervention effect will be represented by an adjusted odds ratio, and will be assessed across different follow-up points. This analysis will be implemented in R using the "glmer()" function, specifying a logit link and a random intercept for participants to account for within-subject correlations.

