# **6.3 Missing Data**

Missing data are expected at follow-up time points (3 months and 6 months) in primary and secondary outcomes. Assuming that the missing data follow a Missing at Random (MAR) pattern, Multiple Imputation by Chained Equations (MICE) (Van Buuren and Groothuis-Oudshoorn 2011) will be used to handle missing values for the primary outcome and secondary outcome adjusting all baseline covariates. Imputations will be generated with 15 datasets using the "mice()" function from the "mice" package in R. The imputation methods will include predictive mean matching (pmm) for continuous outcomes, logistic regression (logreg) for binary outcomes, and polytomous regression (polyreg) for categorical outcomes. Each imputed dataset will be analyzed separately, and results will be combined using Rubin's Rules(Rubin 2004) to obtain pooled estimates and confidence intervals, accounting for the variability within and between imputations.

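### SAP 3.2 allows exclusion after randomisation for choosing not to start PrEP, which can depend on arm; this conflicts with ITT in SAP 4.2, and non-starters without a DBS result would by default be imputed under MAR

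*SAP*

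**What the plan says.** **Order of events.** The protocol (Study procedures, Procedures) randomises men once the baseline survey is done and only then has staff arrange the first clinic visit. SAP 3.2 likewise randomises after consent and screening.

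**Exclusions.** SAP 3.2 aims for 60 men per city but says that "the randomization sequence accommodates up to 70 participants per city", to cover "up to 10 potential exclusions after the initial medical visit due to PrEP contraindications or personal choices to forgo PrEP initiation based on clinical assessments".

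**Analysis set.** SAP 4.2 is one sentence: "The primary analysis for the Prepare Romania trial will follow the intention-to-treat (ITT) principle". It does not mention the men excluded under 3.2.

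**Scoring.** SAP 6.1 defines the primary outcome as a DBS drug level at or above a threshold at 3 and 6 months. It does not mention men who never start. Under SAP 6.3, multiple imputation assuming MAR "will be used to handle missing values for the primary outcome and secondary outcome adjusting all baseline covariates".

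**What differs by arm.** At the first visit, intervention men meet a counsellor about motivation to take up PrEP. They then see the physician, who prescribes to those who want to start. Control men see only the physician (protocol, Intervention Arm and Control Arm). SAP 3.1 states that "the study is unmasked, with both participants and staff aware of group assignments". The protocol's H1 is that intervention men will be more likely to accept PrEP.

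**The concern.** One of the two grounds for exclusion is a behaviour that the intervention is designed to change, and it occurs after randomisation and after contact that differs by arm. If men who decline are dropped, the adherence comparison is conditioned on a post-randomisation outcome. If declining also differs by arm, the groups compared are no longer those that randomisation made comparable. The direction cannot be predicted: counselling that persuades hesitant men to start may lower average adherence among starters while raising the number protected.

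Keeping the men does not by itself settle the matter. A man who never starts and gives no DBS sample has a missing primary outcome. SAP 6.3 would by default impute it from baseline covariates, and starting study PrEP is not one of them. He would tend to receive the adherence of men who did start, and an analysis labelled ITT would return close to the starters-only answer.

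The estimate matters beyond this trial, because SAP 3.3 says that the data are meant to "inform the design of a future effectiveness trial".

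**Working it through.** **Plan's own figures.** The allowance reproduces: 70 − 60 = 10 per city. The standardised effect in SAP 3.3 also reproduces: 0.06/0.32 = 0.1875, which rounds to 0.19. The SAP gives no figure for the effect of the exclusions.

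**Cap on exclusions.** If 10 is per city, as 60 against 70 suggests, the cap is 20/140 = 14.3%. If 10 is the trial total, it is 10/(120 + 10) = 7.7%. Contraindications share this cap, so fewer can be by choice.

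**Assumptions for the illustration.**
- The 6-month rates in SAP 3.3 (92% vs 86%) apply to starters. SAP 3.3 reports them by arm from another trial, so this use is an assumption.
- Men who decline are not protected.
- The split of decliners by arm is assumed, because the documents give none.

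**Formulas.** With n per arm and d decliners, p_I = 0.92 × (n − d_I)/n and p_C = 0.86 × (n − d_C)/n. The difference is p_I − p_C, and OR = [p_I/(1 − p_I)]/[p_C/(1 − p_C)], unadjusted.

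Starters only: 0.92 − 0.86 = +6.0 points; OR = (0.92/0.08)/(0.86/0.14) = 1.87.

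All randomised, n = 70:

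| Decliners (I/C) | p_I | p_C | Difference (points) | OR |
|---|---|---|---|---|
| 2/2 | 0.894 | 0.835 | +5.8 | 1.66 |
| 5/5 | 0.854 | 0.799 | +5.6 | 1.48 |
| 10/10 | 0.789 | 0.737 | +5.1 | 1.33 |
| 3/7 | 0.881 | 0.774 | +10.7 | 2.15 |
| 7/3 | 0.828 | 0.823 | +0.5 | 1.03 |

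Balanced splits move the difference by at most 6.0 − 5.1 = 0.9 points, but they still lower the odds ratio, which is the scale the SAP reports ("The intervention effect will be represented by an adjusted odds ratio", SAP 6.2). The model-based odds ratio will not equal these unadjusted ones.

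**Denominator.** If the sequence is extended only to replace exclusions, 10 decliners imply 130 randomised, or 65 per arm. Then 3/7 gives +11.0 and 7/3 gives +0.1, so the picture is unchanged.

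**Imputation.** Suppose a share f of kept decliners give DBS and the rest are imputed at their arm's observed rate a. Then p = a(n − d)/[(n − d) + f·d]. For the 3/7 split with n = 70:
- f = 0: +6.0, the same as starters only
- f = 0.5: 0.900 − 0.815 = +8.5
- f = 1: +10.7

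**Scale.** The 95% half-width at 60 per arm is 1.96 × √(0.92 × 0.08/60 + 0.86 × 0.14/60) = 0.111, or ±11.1 points. The largest shift in the table is 6.0 − 0.5 = 5.5 points. Only very uneven use of the whole cap would exceed the half-width: 5/15 gives +17.9 and 15/5 gives −7.6. Nothing in the documents suggests such splits.

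**The case against.** **ITT already settles the set.** In its usual sense ITT means all randomised, which points away from removal. A reader might infer that the SAP has decided to drop and replace men who decline. The over-allocation suggests this, but no sentence states it. What stands is that 3.2 speaks of exclusions, 4.2 of ITT, and nothing reconciles them.

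**There is a missing-data rule.** A reader might infer that no rule covers a non-starter without DBS. That is not so: SAP 6.3 covers missing primary outcomes in general. The gap is that nothing in it is specific to non-starters. The SAP does not bar other predictors, such as self-reported adherence, which would lessen the problem where they are recorded.

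**Non-starters may give DBS.** If they did, their outcome would be observed. The protocol's Follow-up Visits text plans biological testing in both arms, but it does not name DBS there and speaks of men who received a prescription. It does not establish that non-starters would give a sample.

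**The aim is adherence, not uptake.** SAP 2.2 aims to "improve adherence to PrEP medication among GBMSM in Romania". The protocol lists uptake and adherence as separate hypotheses and times follow-up from PrEP initiation, whereas the SAP times it from randomisation. A starters' estimand is therefore a choice the sponsor could defend, but it must then be stated and not presented as ITT.

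**The choice rests on clinical assessments.** Physicians review laboratory results in both arms, so part of the choice has the same basis in each. The uptake counselling is still given in one arm only.

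**It is a pilot and sampling error is larger.** Both are true, and they limit the severity. They do not make it sound to leave the analysis set open in an unmasked trial.

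**Conclusion.** The conflict between SAP 3.2 and SAP 4.2 is real. Following 3.2 as written can bias the primary comparison, and keeping the men under 6.3 alone can score non-starters much like starters.

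The size is unknown, because the documents give no uptake by arm. Under the assumptions shown, modest uneven splits move a 6.0-point difference by roughly 5 points either way, and balanced ones by under 1 point. These figures show what is possible, not what is likely, and any decliner protected by PrEP from another source shrinks the gaps. A reader might infer that the plan favours the intervention or invalidates the trial; the documents support neither. For an exploratory pilot this is a should-fix.

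**What to change.** 1. In SAP 3.2 and 4.2, define the primary set as all randomised participants in their assigned arm. Remove personal choice to forgo PrEP as a ground for exclusion from analysis.
2. State how men with a contraindication found at the first visit are handled in the analysis. Either keep them, or exclude them only on facts fixed before arm-specific contact, under one pre-specified rule applied identically in both arms. Report all exclusions by arm and reason.
3. For never-starters (no filled study prescription), use the observed DBS result where there is one. Otherwise count them as below threshold at 3 and 6 months instead of imputing under MAR. Add a sensitivity analysis for those who report PrEP from another source.
4. Report uptake by arm on the same set, and show starters-only adherence as a labelled, non-randomised supplement.

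**Cost.** SAP wording and one derivation rule. Non-starters must stay in the 3- and 6-month surveys already planned and, where they agree, give DBS. Adherence percentages will be lower than among starters, and the primary result will reflect uptake as well as adherence; the supplement keeps the narrower view available. Men who use PrEP from elsewhere and give no DBS may be misclassified, hence the sensitivity analysis.

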# 3.3 Sample Size

The Prepare Romania trial's sample size was chosen to provide preliminary data on the hypothesized intervention outcomes, PrEP adherence and persistence among GBMSM in Romania, as well as to inform the design of a future effectiveness trial. A formal power calculation was not conducted due to the exploratory nature of this pilot study. Instead, we followed guidance from Whitehead et al., which provides recommendations for sample sizes in pilot studies.

The sample size of 60 participants per arm (120 total) was selected based on conservative effect size estimates drawn from previous studies evaluating PrEP adherence interventions. In a comparable RCT testing the SPARK intervention, protective PrEP levels (defined as adherence of ≥4 doses per week) were observed in 94% of the intervention arm and 85% of the control arm at the 3-month follow-up, with corresponding rates of 92% and 86% at 6 months. This difference in adherence rates translates to an estimated effect size of 6%, with a pooled standard deviation of approximately 0.32, yielding a standardized effect size of 0.19. Whitehead et al. suggest a minimum sample size of 25 participants per condition for pilot trials when the effect size falls between 0.1 and 0.3. To ensure adequate power, the Prepare Romania trial conservatively enrolls 60 participants per arm, exceeding this minimum and allowing for a robust assessment of intervention impact.

Each site (Bucharest and Cluj-Napoca) is tasked with recruiting 60 participants. With this sample size, the study expects retention at 6 months to exceed 25 participants per arm, even accounting for potential attrition. This estimate is supported by high retention rates (approximately 89%) reported in prior SPARK trials.

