Aim 2. Explore implementation outcomes to prepare for a future multi-city effectiveness trial. The team will identify individual and institutional barriers to and facilitators of implementing PrEP Romania by applying Proctor et al.'s implementation framework to the analysis of RCT's feasibility and acceptability data, and PrEP counselor, IDP, clinic administrator, and GBM interviews. Results will inform a future effectiveness-implementation hybrid trial of a scaled-up PrEP Romania across several cities.

Research Aims & Abstracts

Hypotheses: Compared to control arm (education only), PrEP Romania participants (counseling, self-directed app use, and in-app text-based adherence support for 6-mos) will be more likely to accept PrEP (H₁); evince better adherence (H₂); and sustain PrEP use across 6-mos (H₃).

STUDY DESIGN

One hundred and twenty GBM will enroll in a 2-arm pilot to test PrEP Romania's (a) feasibility (medical visit attendance), (b) acceptability (intervention staff and GBM interviews about counseling and app usability), and (c) PrEP uptake (filled prescriptions), adherence (self-reported and DBS) and persistence (still on PrEP) at 3- and 6-month follow-ups.

Study Sites: Two of Romania's primary infectious disease (ID) centers in Bucharest and Cluj-Napoca will serve as the study sites. Their IDPs are involved in our ongoing research and treat GBM who test positive for HIV/STIs through our study. They, together with their site psychologists, were part of the team's pilot study for the current RCT, which ended in March 2022.

The National Institute of Infectious Diseases (NIID) Bucharest Clinic. The largest ID university hospital in Romania, NIID is one of 9 regional centers monitoring HIV. NIID monitors all HIV/AIDS cases in Romania, and oversees the other 8 regional centers.

The Cluj-Napoca Clinic. The Regional Center of Evidence and Monitoring of HIV Infection Cluj-Napoca (CREM Cluj) covers 5 jurisdictions in northern Romania. A total of 706 HIV/AIDS patients are registered in CREM Cluj, with 668 being on ART.

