# 4. Statistical Principles

#### 4.1 Confidence Intervals and P-Values

For the Prepare Romania trial, statistical analyses will be conducted with a two-sided significance level set at 0.05. This alpha level applies to all primary and secondary outcomes, ensuring that results are interpreted consistently across study endpoints. The 95% confidence intervals will be calculated for the primary and other key secondary outcomes.

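### SAP 3.3 claims adequate power with no power calculation behind it; on its own rates, 60 per arm gives about 18% (6 months) to 37% (3 months)

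*SAP*

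**What the plan says.** SAP section 3.3 opens by saying that the sample size is meant to yield preliminary data and inform a later trial, and that "A formal power calculation was not conducted due to the exploratory nature of this pilot study". In place of power it relies on published pilot guidance, said to "suggest a minimum sample size of 25 participants per condition for pilot trials" when the standardized effect lies between 0.1 and 0.3. The planning rates come from an earlier randomized trial of the counseling intervention: 94% vs 85% at 3 months, "with corresponding rates of 92% and 86% at 6 months". From these the SAP carries forward a 6-point effect, a standard deviation of about 0.32 and a standardized effect of 0.19.

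The same paragraph then says: "To ensure adequate power, the Prepare Romania trial conservatively enrolls 60 participants per arm, exceeding this minimum", and adds that this size is "allowing for a robust assessment of intervention impact".

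Elsewhere, section 4.1 states that "statistical analyses will be conducted with a two-sided significance level set at 0.05" and applies that level to all primary and secondary outcomes. Section 6.2 says that the binary primary outcome "will be analyzed using a GLMM with a logit link function". The protocol, under Study Design, also describes a pilot: "One hundred and twenty GBM will enroll in a 2-arm pilot".

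**The concern.** A plan cannot both disclaim a power calculation and justify its size by power. No target power, formula or power figure appears anywhere in section 3.3, so the claim rests only on 60 being larger than 25. A pilot minimum is not a power criterion: on the 6-month rates, 25 per arm gives about 10% power.

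What is at stake is how the result will be read. Section 2.2 sets the aim as evaluating effectiveness, and section 4.1 attaches a 0.05 test to the primary outcome. A reader who accepts that power is adequate would give a non-significant primary result weight that it cannot carry, including when the data are used to plan the next trial.

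**Working it through.** **Inputs.** Rates of 94% vs 85% and 92% vs 86%, 60 per arm, retention of about 89% (SAP 3.3); two-sided 0.05 (SAP 4.1); 1:1 allocation (SAP 3.1); binary outcome at 3 and 6 months (SAP 6.1). Retained per arm: 0.89 × 60 = 53.4, taken as 53.

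**The SAP's own figure.** 0.06 / 0.32 = 0.1875, which rounds to the stated 0.19. From the 6-month rates, SD = √[(0.92×0.08 + 0.86×0.14)/2] = 0.311 and 0.06/0.311 = 0.193. The standardized effect is correct. There is no stated power to reproduce.

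**Single-visit power.** With p̄ the mean of the two rates and D their difference,

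power ≈ Φ{ [D − 1.96·√(2p̄(1−p̄)/n)] / √[(p1(1−p1) + p2(1−p2))/n] }.

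- 92% vs 86%, n = 60: (0.06 − 0.1120)/0.0569 = −0.914, so 18.0%.
- 94% vs 85%, n = 60: (0.09 − 0.1097)/0.0554 = −0.356, so 36.1%.

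Exact enumeration of the same pooled test agrees:

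| Rates | n = 60 | n = 53 |
|---|---|---|
| 92% vs 86% | 17.9% | 16.2% |
| 94% vs 85% | 36.6% | 32.7% |

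Fisher's exact test is lower (11.0% and 25.2% at 60 per arm).

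**Size for 80% power.** n = [1.96·√(2p̄(1−p̄)) + 0.8416·√(p1(1−p1) + p2(1−p2))]² / D².

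- 92% vs 86%: (0.8673 + 0.3707)² / 0.0036 = 425.7, about 426 per arm.
- 94% vs 85%: (0.8497 + 0.3609)² / 0.0081 = 180.9, about 181 per arm.

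Conversely, from an 86% control rate, 60 per arm reaches 80% power only if the intervention rate is about 99%.

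**Precision.** 95% CI half-width for the risk difference, 92% vs 86%: 1.96·√(0.194/60) = 0.111, and 0.119 at 53 per arm (for 94% vs 85%: 0.109 and 0.116). The half-width is nearly twice the 6-point effect. As an unadjusted odds ratio: (0.92/0.08)/(0.86/0.14) = 1.87. The standard error of its logarithm is √(1/55.2 + 1/4.8 + 1/51.6 + 1/8.4) = 0.604, so the 95% CI is about 0.57 to 6.1.

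**Both visits together.** The mean difference is (9 + 6)/2 = 7.5 points. For within-person correlation ρ, which the documents do not give, the variance of the difference is (0.3779 + 2ρ × 0.1883)/(4n). Normal approximation:

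| ρ (assumed) | n = 60 | n = 53 |
|---|---|---|
| 1.0 | 27% | 24% |
| 0.5 | 34% | 31% |
| 0.3 | 38% | 34% |
| 0 | 47% | 43% |

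For 80% power the two-visit average needs about 171 (ρ = 0.3) to 263 (ρ = 1.0) per arm.

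**Closer to the planned model.** A random-intercept logistic model was simulated with two visits, complete data, no covariates, and a likelihood-ratio test of the average of β2 and β4. There were 1,500 trials per scenario, with Monte Carlo error of about ±2.5 points. Power was 36% to 42% at 60 per arm and 31% to 38% at 53, for an assumed correlation of 0.6 to 0.3; it was about 47% at 60 per arm for independent visits. Type I error was 5.3% to 5.7%. A Wald test gave 33% to 36% at 60 per arm for the same correlations.

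**The case against.** The strongest reply is that section 3.3 already discloses what matters. It calls the study a pilot, says that no power calculation was made and promises no power level. On that reading the disputed words are loose phrasing for an adequate pilot size, no figure in the SAP is wrong, and the required 95% confidence intervals will show the imprecision anyway. It is also fair that the rates are borrowed from another trial, so power for the true effect in this population is unknown, and that the two-visit figures rest on an assumed correlation and leave out the planned covariates and multiple imputation.

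Much of this stands. The flaw is a false statement, not a miscalculated number, and the single-visit figures alone are enough to show it. But the earlier disclaimer does not cure the later claim; it contradicts it. The borrowed rates are the ones that the SAP itself chose as the basis for its sample size.

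One limit should be explicit. Power is below 50% in every two-sided variant computed at 60 and 53 per arm, although the simulated value for independent visits is within Monte Carlo error of 50%. At 70 per arm, the ceiling of the randomization sequence in section 3.2, the two-visit approximation reaches about 53%, but only if a person's two visits are independent; at a correlation of 0.3 it is 43%. None of these is near 80%.

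**Conclusion.** The concern holds. Section 3.3 contradicts itself and credits the design with a property that it lacks. For the 6-point effect that the SAP carries forward, a single-visit test at 60 per arm would miss the difference in about four of five trials (1 − 0.18 = 0.82); for the 3-month difference, in nearly two of three (1 − 0.37 = 0.63). Using both visits helps but does not rescue the claim.

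The single-visit results need only the SAP's rates, its two-sided 0.05 level and an unadjusted comparison. The two-visit results also need the assumed correlation. The effect of covariate adjustment and imputation on power was not assessed. The sample size itself is not criticised: 60 per arm is defensible for a pilot that is described as one.

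**What to change.** In SAP 3.3, remove the opening purpose clause of the sentence "To ensure adequate power, the Prepare Romania trial conservatively enrolls 60 participants per arm, exceeding this minimum" and its closing claim, "allowing for a robust assessment of intervention impact". Keep 60 per arm. Replace them with, for example:

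*The sample size is not based on power. As unadjusted single-visit approximations on the risk-difference scale (two-sided 0.05), 60 per arm gives about 18% power for 92% vs 86% and about 37% for 94% vs 85% (about 16% and 33% at 53 per arm), with a 95% CI half-width of about 11 points (about 12 at 53 per arm). Averaged over both visits, power is roughly 27% to 38% (24% to 34% at 53 per arm), assuming a within-person correlation of 1.0 to 0.3.*

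The last sentence can be dropped if the sponsor prefers not to print figures that depend on an assumed correlation.

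As optional good practice, section 4.1 could add that the primary result is read from the estimate and its 95% CI, and that p > 0.05 is not taken as absence of effect.

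The cost is SAP wording only. The stated property becomes less favourable; sample size, analysis and conduct do not change.
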